4.1 Endpoints

4.1.1 Part A

The primary endpoint for safety is the incidence of AEs (overall or grouped as neurological, psychiatric or cardiovascular).

The hypothesis for the primary endpoint for safety is that ABvac40 will be safe for human administration, according to the observed pattern of AEs. The trial will be considered satisfactory if the pattern of AEs (overall or grouped as neurological, psychiatric or cardiovascular) is consistent with a good safety and tolerability profile of ABvac40 for human administration at the final visit.

Additionally, the following secondary safety endpoints will be evaluated including:

- number of withdrawn patients due to adverse events (AEs)
- number of withdrawn patients due to other causes
- number of serious adverse events (SAEs)
- number of clinically significant changes in physical and neurological examination
- number and type of concomitant medications
- number of clinically significant changes in vital signs (blood pressure, heart rate, respiratory rate, body temperature), body mass (weight, height).
- number of clinically significant changes in brain MRI
- number of clinically significant changes in electrocardiogram (EKG)
- number of clinically significant changes in analytical haematology, biochemistry, coagulation, serology and urine test strip results.

The primary efficacy endpoint is the average maximal increment ($M\Delta$) of anti-A β 40 antibody signal (OD in ELISA) in each subject with regard to the pre-treatment visit (either V0 or V1).

For the primary efficacy analysis, the trial will be considered successfully confirmatory regarding efficacy (immunogenicity) of ABvac40 if the average maximal increment ($M\Delta$) of anti-A β 40 antibody signal (OD in ELISA) in the verum group is >0 OD than the average $M\Delta$ in the placebo group. For the secondary efficacy analysis, the trial will be considered satisfactory if the difference of the average maximal increment ($M\Delta$) of anti-A β 40 antibody signal (OD in ELISA) in the treated group is > 1.778 OD than the average $M\Delta$ in the placebo

group; the difference that was reached between both groups in the phase I clinical trial of ABvac40.

Additionally, the following secondary efficacy endpoints will be evaluated including:

- Characterization of the immune response:
 - o Levels of anti-KLH and anti-A β 42 antibodies in plasma
 - o Level of anti-A β 40 antibodies in CSF

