9.1.3.1 Primary Safety Analysis

The primary safety variable is the frequency (%) of Adverse Events (AEs). The primary safety endpoint will be analyzed descriptively in the Safety population. For this primary safety analysis, the amyloid-PET negative and the amyloid-PET positive subjects within each treatment group will be pooled together.

The trial will be considered satisfactory if the pattern of AEs (overall or grouped as neurological, psychiatric or cardiovascular) is consistent with a good safety and tolerability profile of ABvac40 for human administration.

All AEs will be coded using the last version of the MedDRA dictionary where neurological AEs corresponds with the System Organ Class (SOC) Nervous system disorders, psychiatric AEs corresponds with the SOC Psychiatric disorders, and cardiovascular SOC corresponds with Vascular Disorders and Cardiac disorders.

The number and percentage of patients in each treatment group reporting at least 1 occurrence of an AE for each unique SOC and PT will be tabulated. AEs will be also tabulated by severity and by the relationship to study medication in each treatment group as assessed by the investigator. Patients who experienced multiple adverse events with the same PT will be counted once for the summaries, using the worst severity. Specific tables will be provided for AEs of special interest such as neurological, psychiatric and cardiovascular AEs.

As an exploratory analysis, the incidence of AEs (overall or grouped as neurological, psychiatric or cardiovascular) will be compared between the group receiving the active treatment (ABvac40) and the control group receiving placebo. Fisher's exact test will be used for these analyses.

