Emergent SAESIs, Treatment related TESAEs, TESAEs leading to treatment discontinuation and TESAEs leading to death.

Counts and percentages of patients will be presented by treatment group, SOC and PT for the following: TEAEs, non-TEAEs, TEAEs leading to study withdrawal, Treatment-Emergent SAESIs and TESAEs.

Counts and percentages of patients with TEAEs will be presented by treatment group, SOC, PT and maximum causality.

Counts and percentages of patients with TEAEs will be presented by treatment group, SOC, PT and maximum severity.

For summaries by maximum causality/severity, if a patient reported more than one AE with the same PT, the AE with the maximum causality/severity will be presented. If the causality/severity of an AE is missing, the causality/severity will be treated as missing in summaries. If a patient reported more than one AE within the same SOC, the patient will be counted only once under the maximum causality/severity within the SOC.

The denominator for the percentages for the ABvac40 group will be all patients in both the ABvac40 arm Part A / Placebo+Booster arm Part B and Placebo arm Part A / ABvac40 arm Part B treatment sequences who took at least one dose of ABvac40 throughout the study.

The denominator for the percentages for the Placebo group will be all patients in both the ABvac40 group Part A / Booster group Part B and the Placebo arm Part A / ABvac40 arm Part B treatment sequence who took at least one dose of Placebo.

In Part B, the safety population will be those subjects who received at least one dose.

AEs will be listed by treatment group and patient identifier. In addition, patients with SAEs and AEs leading to premature discontinuation of treatment period from the study will be individually listed.

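### SAP 7.2.1 leaves out, undeclared, the protocol's grouped adverse-event tables and exploratory Fisher comparison for the Part A primary safety endpoint, and specifies no table for the concurrent Part A groups

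*SAP*

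**What the plan says.** Protocol 4.1.1 sets the endpoint: "The primary endpoint for safety is the incidence of AEs (overall or grouped as neurological, psychiatric or cardiovascular". Protocol 9.1.3.1 then does four things.

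- It makes the analysis descriptive: "The primary safety endpoint will be analyzed descriptively in the Safety population".
- It maps the groups to MedDRA: "neurological AEs corresponds with the System Organ Class (SOC) Nervous system disorders", psychiatric events to the Psychiatric disorders class, and "cardiovascular SOC corresponds with Vascular Disorders and Cardiac disorders".
- It promises displays: "Specific tables will be provided for AEs of special interest such as neurological, psychiatric and cardiovascular AEs".
- It adds an exploratory comparison of ABvac40 with placebo, overall and by group, for which Fisher's "exact test will be used for these analyses".

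The success statement in the same section opens: "The trial will be considered satisfactory if the pattern of AEs (overall or grouped as neurological, psychiatric or cardiovascular) is consistent with a good safety". It sets no threshold, margin or significance level.

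SAP 7.2.1 plans an overall summary that includes patients with any TEAE, and then: "Counts and percentages of patients will be presented by treatment group, SOC and PT for the following: TEAEs, non-TEAEs" and some further categories. It names none of the three groups and no test. In SAP 4.1.1, special interest covers only serious ARIA and aseptic meningo-encephalo-myelitis.

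SAP section 3 says that AE summaries run across Parts A and B. Under 7.2.1, the ABvac40 denominator takes every patient from either sequence with any ABvac40 dose, and the placebo denominator does the same for placebo. SAP 9.2 lists departures from the protocol without mentioning any of this. SAP 1.1 gives the SAP precedence where the two documents differ.

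**The concern.** Safety is one of the two primary endpoints of Part A. The protocol named the groupings in advance and reported phase I in the same groups with Fisher p-values (Protocol 2.2, Table 1). The stated purpose of phase II is to confirm that safety level. A SAP rewritten as a stand-alone document that takes precedence over the protocol should carry the groupings forward or record that they were dropped.

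Two things are at stake. One component of the endpoint, cardiovascular incidence, has no summary row of its own. And the columns in which the other components appear are not the two concurrent Part A groups, so the randomised comparison is not visible in any table that the SAP text specifies.

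**Working it through.** **The plan's own figures.** The rule of three gives n = 3/0.05 = 60 per group. With 60 patients and a true rate of 5%, the chance of seeing at least one event is 1 − 0.95^60 = 0.954, which agrees with the stated 95%. Fisher's exact test on the phase I counts (16 ABvac40, 8 placebo) also reproduces the p-values in Protocol Table 1.

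| Group | ABvac40 | Placebo | Fisher p |
|---|---|---|---|
| Overall | 11/16 | 7/8 | 0.6214 |
| Neurological | 5/16 | 5/8 | 0.2038 |
| Psychiatric | 2/16 | 1/8 | 1.000 |
| Cardiovascular | 1/16 | 1/8 | 1.000 |

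**What the SAP's summary tables show.**

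| Component | Where it appears in the SAP | Readable? |
|---|---|---|
| Overall | any-TEAE line | yes |
| Neurological | Nervous system disorders row | yes |
| Psychiatric | Psychiatric disorders row | yes |
| Cardiovascular | Cardiac and Vascular rows, separately | bounds only |

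With a cardiac patients, b vascular patients and n in the column, the number with either lies between max(a, b) and min(n, a + b). Assume a = 5, b = 6, n = 60. The bounds are 6 and 11 patients, that is 6/60 = 10.0% to 11/60 = 18.3%. Against an assumed 3/60 in the other group, two-sided Fisher p depends on the overlap:

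| Patients with either | Fisher p against 3/60 |
|---|---|
| 6 | 0.49 |
| 7 | 0.32 |
| 8 | 0.20 |
| 9 | 0.13 |
| 10 | 0.075 |
| 11 | 0.043 |

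**What the columns contain.** The documents do not say how many patients enter Part B. Let m per arm enter and receive both products over the study, starting from 60 per arm. Each AE column then has 60 + m patients, and 2m of the 120 count in both columns.

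| m (assumed) | Each column | In both columns | Share of 120 |
|---|---|---|---|
| 30 | 90 | 60 | 50% |
| 35 | 95 | 70 | 58% |
| 60 | 120 | 120 | 100% |

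Events move too. Outside the special-interest category, 7.2.1 assigns an event to the last injection received. A patient given ABvac40 in Part A therefore contributes to the placebo column for events after a Part B placebo injection and before the booster.

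**What a restored comparison could show.** Assume 60 v 60 and a two-sided 5% level (the protocol sets no level for this test). The smallest significant splits are then 6 v 0, 8 v 1, 10 v 2 and 11 v 3. Power is about 33% for 15% v 5% and about 85% for 25% v 5%. The test can only support a descriptive reading.

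**The case against.** The strongest reply has five parts.

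- A reader might infer that the primary safety endpoint has been dropped. It has not: by the protocol's own mapping, three of its four components stay visible. This stands.
- A reader might infer that the safety success criterion can no longer be assessed. The criterion is a judgement on a pattern, with no threshold. The Fisher comparison is labelled exploratory in 9.1.3.1, and the synopsis puts it under secondary safety analysis. Losing it cannot block the criterion, whose vagueness comes from the protocol. This stands.
- A reader might count the missing confidence interval for the AE difference as a departure. The protocol never promised one. This stands.
- The SAP lists AEs by patient, so if the listing shows coded terms the cardiovascular count can be derived by hand. That is true, but a component of a primary endpoint should not depend on a hand count.
- The SAP supplements the protocol and keeps table specifications in separate documents, so silence is not deletion. SAP 2.3 also foresees a separate lock and report for Part A, so a Part A run of the AE tables may be intended. This is possible and cannot be excluded from the text. But section 3 frames AE summaries across both parts. Section 7.3.4 asks for Part A, Part B and combined tables for concomitant medication, while 7.2.1 asks for no such split. SAP 9.2 records other changes, such as an added plasma antibody outcome, but not this one.

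**Conclusion.** The point holds as an undeclared omission, at should-fix level. The SAP text leaves out the protocol's group tables and exploratory Fisher comparison. Cardiovascular incidence is only bounded by the specified summary rows (6 to 11 of 60 in the example). No specified table shows the endpoint for the concurrent Part A groups, because the columns pool both parts and count crossed-over patients twice.

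The documents do not support the stronger claims that the endpoint is abandoned or the success criterion unreadable. No primary inference, sample size or data collection changes.

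The AE counts and Part B entry numbers are assumptions, chosen only to show the range. The conclusion rests on the SAP text; the table specifications, which are separate documents, could already contain what is missing.

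**What to change.** Add to SAP 7.2.1 one Part A-only table in the Safety Analysis Set, by Part A treatment received, in line with SAP 3.1.5. Give the number and percentage of patients with at least one TEAE:

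- overall;
- in Nervous system disorders;
- in Psychiatric disorders;
- in Cardiac or Vascular disorders combined, each patient counted once.

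Include the protocol's Fisher p-value, labelled exploratory. A risk difference with a 95% CI would be useful descriptive support but is optional. State how a patient who received both products within Part A is placed, because the general rule in SAP 3.3 excludes AE summaries. Keep the pooled tables as an additional display.

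If the group tables or the comparison are left out on purpose, say so in 9.2 and give the reason. The cost is a few lines of SAP text and one table from data already collected.

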3.1 Part A (Randomized, Double-Blind, placebo-controlled – 18 to 24 months follow-up)

3.1.1 Safety Objectives

3.1.1.1 Primary Safety Objective

- To evaluate the safety and tolerability of repeated doses of ABvac40 in a population of patients with a-MCI or vm-AD.

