4.9.1.2 Selection and Active Phase: visits V1-V21 (weeks 0-50)

Eligible patients will be randomized at baseline visit (V1).

The Inclusion Visit (V1) should be performed in 2 separate days; the vaccination should take place **at least 3 days** after the CSF extraction, **or the time needed until resolution of any AE occurring after the CSF extraction, whichever is longer** (to avoid interference with the assessment of AEs related to the vaccination), **with a maximum of 10 days after the urine and blood sample extraction:**

- Day 1 of V1 (V1a):
 - Urine analysis, blood sample extraction (for ApoE genotyping, hemogram, biochemistry and biological activity) and CSF collection
- Day 2 of V1 (V1b):
 - Physical and neurological exam, neuropsychological battery and IGE, quality of life, vital signs (before vaccination), vaccination, vital signs (after vaccination), concomitant medication and AEs.

The Active Phase period consist in two different types of visits: vaccination visits (V1, V4, V7, V10, V13 and V18) and safety visits (phone interview: V2, V5, V8, V11, V14, V19 and face-to-face visits: V3, V6, V9, V12, V15, V16, V17, V20 and V21).

Data to be recorded in the eCRF (and corresponding source documents), at the Vaccination Visits (V1, V4, V7, V10, V13 and V18):

- Medical Evaluation
 - o Physical and neurological examination
 - o Vital signs (blood pressure, heart rate, respiratory rate, body temperature) before and after the Vaccination
 - o Corporal biometry (weight)
- Medical History:
 - o Record relevant past and concomitant diseases
 - o Record concomitant medication.
 - o Record any adverse events.
- Randomization at Visit 1.
- Lumbar puncture to obtain CSF, only at V1.
- Treatment:
 - o Administer the study treatment
 - o Assess vaccine reaction, local and systemic.
 - o 2 hour after vaccination vital signs and a thorough examination of the patient to assess any reaction to the vaccine will be carried out and any adverse events (AEs) recorded.
- Neuropsychological Battery (V1; only ADS-ADL MCI and TMT)
- Quality of Life EQ-5D-5L (V1)
- Laboratory tests (hemogram, biochemistry and biological), and ApoE genotyping (only at V1).
- COVID-19 PCR test result (only at V16)

Data to be recorded in the eCRF (and corresponding source documents) at the safety phone interview (V2, V5, V8, V11, V14 and V19):

- Medical History:
 - o Local or systemic reactions to the vaccine
 - o Concomitant Medication
 - o Adverse events

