8.2.7 Patient's Diary and Patient emergency card

Study subjects will be provided with a "Patient Diary" (PD). This will be used to record body temperature, local reactions to the treatment or any other AE. Furthermore, the subject will be required to record in the PD any concomitant medication including changes in the conventional treatment of AD.

The patient/caregiver will be told to come to subsequent visits with the patient diary completed. The researcher will transcribe information recorded by the patient/caregiver in the relevant pages of the eCRF. The patient's original diary will be kept at the trial center along with the original documents.

Upon inclusion in the study, each patient and their caregiver will receive a "patient card" stating that they are participating in a clinical trial, identified by its code, title, and name of the study drug. The name, address and emergency telephone number (available 24 hours) of the responsible investigator will be printed on the card along with a request to contact the investigator in case of emergency. If a patient suffers a serious adverse event and needs to go to hospital, they should go to the nearest hospital possible; the patient and caregiver will be advised to carry the "patient card" with them at all times during the study, as a safety measure.

8.3 Procedures for Eliciting Reports of and for Recording and Reporting Adverse Event and Intercurrent Illnesses

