8.3.10.2 Reactions to the vaccine

Reactions to the vaccine may vary from mild to severe reactions (shock or anaphylaxis) that can cause death. If such a severe reaction is suspected, patients will be observed for 24 hours in the study center after administration of the vaccine (overnight hospitalization) and before being discharged vital signs and a thorough examination will be recorded to assess any reaction to the vaccine (see Appendix 1).

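### The SAP plans no summary of the separately recorded vaccine reactions and no AE or reaction summary by injection number, so its AE tables cannot show a change in tolerability from dose 1 to the booster

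*SAP*

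**What the plan says.** **Objective.** Protocol 3.1.1.1 sets the primary safety objective: "To evaluate the safety and tolerability of repeated doses of ABvac40 in a population of patients with a-MCI or vm-AD".

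**What is recorded.** Protocol 4.9.1.2 lists the eCRF content for Part A.
- Vaccination visits (V1, V4, V7, V10, V13, V18): "Assess vaccine reaction, local and systemic", and "2 hour after vaccination vital signs and a thorough examination of the patient to assess any reaction to the vaccine will be carried out", with any AEs recorded in the same step.
- Telephone calls and safety visits: "Local or systemic reactions to the vaccine" has its own line, apart from the AE line.
- Protocol 4.9.2 repeats this for Part B.

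Protocol 8.2.7 says of the diary: "This will be used to record body temperature, local reactions to the treatment or any other AE". Its entries are transcribed to the eCRF. Protocol Appendix 1 defines local reactions by size and time of onset and grades systemic reactions from 1 to 5.

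**What is planned.** SAP 7.2.1 says of the AE tables: "Counts and percentages of patients will be presented by treatment group, SOC and PT for the following", and then lists the AE categories. Further tables give TEAEs by maximum causality and maximum severity. SAP section 3 has AE summaries run across both parts under two labels, ABvac40 and Placebo. The most recent injection before a non-SAESI event is used only to choose the label. The denominators are patients with at least one dose of the product concerned. Local and systemic reactions, the Appendix 1 grades, the diary and the injection number do not appear as outputs anywhere in the SAP text.

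**The concern.** For a repeated conjugate vaccine, a main tolerability question is whether reactions become more frequent or stronger with later doses. It is sharper here because Protocol 2.2 describes Phase I as two injections, with a third added by amendment, and Protocol 2.4.2 justifies two further monthly injections and a booster. Doses 4 to 6 therefore go beyond the Phase I exposure. Protocol 3.2.2.2 also aims, as an exploratory Part B objective, to define the best treatment scheme.

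A table that counts a patient once per preferred term over the whole study cannot show at which dose the event occurred. A maximum-severity table shows the worst event but not when it happened. Patients in both sequences receive both products by the end of Part B, so the same patient can be in both AE denominators. The combined table is therefore not a comparison of the randomised arms in Part A.

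Some reactions may also never reach the AE tables. Appendix 1 does not treat site erythema, pruritus or hyperaemia as an adverse reaction, and for adults it requires a wheal above 5 cm (immediate) or 10 cm (delayed). How far milder reactions are also entered as AEs cannot be told from the documents.

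**Working it through.** **1. The plan's own safety figure.** Protocol 9.2 and SAP 3.2 give 60 per arm for at least 95% probability of seeing an AE with a 5% rate.
- Rule of three: 3 / 0.05 = 60.
- Exact: 1 − 0.95^60 = 0.954. The smallest n that reaches 0.95 is 59 (0.9515).

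The figure reproduces. No number in the documents is wrong on this point.

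**2. Which planned outputs are by visit or injection.**

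| Output | SAP section | Resolution | What it shows about reactions |
|---|---|---|---|
| AE tables | 7.2.1 | None; pooled over injections and parts | Terms, worst severity, worst causality |
| Vital signs, including temperature | 7.3.5 | Timepoint within visit | Before and about 2 hours after each injection |
| Physical and neurological examination | 7.3.2, 7.3.3 | Visit | Normal/abnormal shift |
| Laboratory values, including C-reactive protein | 7.3.7 | Visit | Values and shifts |
| Local and systemic reaction items | – | No output | – |
| Diary | – | No output | – |

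**3. Volume of data without a planned summary.** Each Part A injection is followed by three reaction assessments: at 2 hours, by telephone, and at the safety visit two weeks later. With 60 patients per arm and six injections, 6 × 60 = 360 injections and 360 × 3 = 1,080 assessments per arm. This is a maximum, before any dropout.

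**4. What counting a patient once conceals.** The rates below are assumptions, with independence between doses. The share of patients with the event at any dose is 1 − Π(1 − p_k).
- Rising 5, 10, 15, 20, 25, 30%: 1 − (0.95 × 0.90 × 0.85 × 0.80 × 0.75 × 0.70) = 1 − 0.305 = 69.5%.
- Flat 18%: 1 − 0.82^6 = 1 − 0.304 = 69.6%.
- Flat 5%: 1 − 0.95^6 = 26.5%. A profile of 0% at doses 1 to 5 and 26.5% at dose 6 gives the same 26.5%.
- Range for a flat rate over six doses: 1% per dose gives 5.9%, and 10% gives 46.9%.

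**5. What a by-injection table could support.** The chance of seeing at least one case of a 5% reaction at a given dose is 1 − 0.95^n.
- Dose 1, n = 60: 95.4%.
- Late dose, if all of the expected 40% dropout comes before it, n = 35 or 36: 83.4% or 84.2%.
- With no reactions seen, the one-sided 95% upper bound, 1 − 0.05^(1/n), is 4.9% at n = 60, 8.0% at n = 36 and 8.2% at n = 35.

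**The case against.** **The AE rate is the primary safety variable, and no reaction table was promised.** This stands. Protocol 8.1 and 9.1.3 define the primary safety variable through AEs and plan no reaction table. A reader might infer that SAP 9.2 hides a departure from the protocol. It does not: that section lists changes to protocol-specified analyses, and there is none here to list.

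**Tolerability is not seen through AE terms alone.** This stands too. The by-visit outputs in the table above follow the injection schedule closely. They do not show later fever, local reactions by size, or systemic reactions by grade.

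**Reactions may already become AEs.** Largely fair. AEs are recorded in the same step as the 2-hour check, Protocol 8.2.7 words local reactions as a kind of AE, and Protocol 8.2.4 makes new examination findings AEs. A reader might infer that reactions not re-entered as AEs are lost; the documents do not establish how many, if any, are. Even if every reaction is an AE, the AE tables still pool all injections.

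**The illustrative rates were chosen to coincide, and no planned table has an any-reaction row.** True. They show what is possible and are not an estimate. The same arithmetic applies to a single preferred-term row, which the plan does have.

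**Other routes exist.** Table specifications are in separate documents (SAP 1.1), AEs are listed by patient, and listed dates carry the study day. SAP 2.3 also foresees a Part A lock and report. Tables run on Part A data alone would in effect be by arm, but would still pool six injections. Listings allow case review but are not a summary by arm.

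**Conclusion.** The gap holds for the SAP text. No summary of the separately recorded local and systemic reactions or of the diary is planned, and no AE or reaction summary by injection number. A change in tolerability between dose 1 and the booster cannot be read from the planned AE tables, although tolerability of repeated doses is part of the primary safety objective. In the assumed example, profiles as different as 5% rising to 30% and a flat 18% both appear as about 70%.

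Three stronger readings go beyond the documents:
- *Diary temperatures are taken around every injection.* Protocol 8.2.7 gives no diary schedule, so a by-injection temperature table may not be possible.
- *Protocol 8.3.10.2 makes reactions an analysis variable.* It states "Reactions to the vaccine may vary from mild to severe reactions (shock or anaphylaxis) that can cause death" and then covers observation when a severe reaction is suspected. It creates no endpoint.
- *1,080 assessments per arm will be unused.* That is a ceiling, which assumes 60 patients per arm receive all six injections.

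The conclusion assumes that the separate table specifications do not already contain such a table. It concerns reporting, not clinical management. It is a worthwhile low-cost addition and not an error in the primary analysis.

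**What to change.** Add to SAP 7.2:
1. **Part A table** by randomised arm and injection number (V1, V4, V7, V10, V13, V18): patients with any local and any systemic reaction, by type and by maximum severity or grade as recorded. The denominator is the patients given that injection.
2. **Fallback.** Where reactions were captured only as AEs, use TEAEs with onset between that injection and the following safety visit (V3, V6, V9, V12, V15, V20).
3. **Part B table** by treatment sequence, with V13B shown separately because it is the only ABvac40 injection in Part B for patients first randomised to ABvac40.
4. **Diary temperature** by injection, only if the diary dates allow it.

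**Cost.** Some extra table specification and programming from items the protocol already requires. How finely type and severity were captured has to be checked against the eCRF. AEs with partial onset dates need a stated rule or an unassigned row. Late-dose denominators will be small after dropout (35 or 36 per arm in the worst case above), so the table should be read descriptively. No sample size, visit or treatment rule is affected.
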